5.3 Abnormality criteria for laboratory, ECG and vital sign

Table 5-3 Liver Abnormality Criteria

Liver events defined by laboratory parameter abnormalities (additional non-lab criteria as provided in the protocol are ignored):

Parameter	Criterion
For each assessment:	ALT > 3x ULN ALT > 5x ULN ALT > 8x ULN ALT > 10x ULN ALT > 20x ULN ALT or AST > 3x ULN ALT or AST > 5x ULN ALT or AST > 8x ULN ALT or AST > 10x ULN ALT or AST > 20x ULN ALT or AST > 3x ULN & TBL > 1.5x ULN ALT or AST > 3x ULN & TBL > 2x ULN ALP > 1.5x ULN

Parameter	Criterion
	ALP > 2x ULN ALP > 3x ULN ALP > 5x ULN TBL > 1x ULN TBL > 1.5x ULN TBL > 2x ULN TBL > 3x ULN ALP > 3x ULN & TBL > 2x ULN ALP > 5x ULN & TBL > 2x ULN ALT or AST > 3 × ULN and INR > 1.5 Potential Hy's Law cases (defined as ALT or AST > 3 × ULN and Total bilirubin > 2 × ULN and ALP ≤ 2 × ULN) Any clinical event of jaundice (or equivalent term)
If ALT or AST abnormal at baseline:	ALT or AST > 2x baseline or > 300 U/L (whichever occurs first)

Table 5-4 Renal Abnormality Criteria

Criterion

 Serum creatinine increase 25 - <50% compared to baseline Serum creatinine increase ≥ 50% compared to baseline New dipstick proteinuria ≥3+ New dipstick hematuria ≥3+ Protein-creatinine ratio (PCR) ≥ 1g/g Cr (or mg/mmol equivalent as converted by the measuring laboratory)*

*Creatinine is not tested in urine according to protocol so urine PCR is not available in central lab data.

Table 5-5 ECG Abnormality Criteria

ECG Parameter	Abnormality Flags	
	Absolute	Relative*

RR Interval	Low: < 600 msec ; High: > 1200 msec	Low: ≤ -20%; High: ≥ 20%
PR interval	Low: < 120 msec ; High: > 200 msec	Low: ≤ -20%; High: ≥ 20%
QRS Interval	Low: < 60 msec ; High: > 109 msec; High: > 120 msec	Low: ≤ -20%; High: ≥ 20%; High: ≥ 25%
QT Interval	Low: < 320 msec ; High: ≥ 450 msec for male, ≥ 460 for female; >500 for both	>30 to ≤ 60 msec, >60 msec
QTcF Interval (Fridericia's correction)	Low: < 320 msec ; High: ≥ 450 msec for male, ≥ 460 for female; >500 for both	>30 to ≤ 60 msec, >60 msec
*Relative change from previous pre-dosing measurement in percent (%) for RR, PR, QRS, relative change in values compared with previous pre-dosing measurement in millisecond (msec) for QTcF Interval and QT intervals.		

Table 5-6 Vital Signs Abnormality Criteria

Variable	Criterion value	Change relative to baseline
Heart rate/pulse	> 120 bpm* < 50 bpm	increase of ≥ 15 bpm decrease of ≥ 15 bpm
Systolic blood pressure	≥ 200 mm Hg > 180 mm Hg < 90 mm Hg	increase of ≥ 20 mm Hg increase of ≥ 40 mm Hg decrease of ≥ 20 mm Hg
Diastolic blood pressure	≥ 120 mm Hg > 105 mm Hg < 50 mm Hg	increase of ≥ 15 mm Hg increase of ≥ 25 mm Hg decrease of ≥ 15 mm Hg
Weight	Baseline weight (kg)	increase of ≥ 7% decrease of ≥ 7%

*bpm= beats per minute

6 Reference

Ecevit E (2008), Usage of Penalized Maximum Likelihood Estimation Method in Medical Research: An Alternative to Maximum Likelihood Estimation Method. *JRMS* 2008; 13(6): 325-330

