## **9 Study discontinuation and completion**

### **9.1 Discontinuation and completion**

#### **9.1.1 Study treatment discontinuation and study discontinuation**

Discontinuation of study treatment for a participant occurs when study treatment is stopped earlier than the protocol-planned duration. Discontinuation of study treatment can be initiated by either the participant or the investigator.

Discontinuation of study treatment may or may not include study drug infusion interruption, i.e. shortening of the infusion to less than 40 minutes. If the duration of an infusion is shortened, the next planned infusion should be planned to be administered for the full 40 minutes. If there is a concern that the participant cannot tolerate the full duration of the infusion the investigator should consider permanent discontinuation of study treatment.

The investigator must discontinue study treatment for a given participant if, he/she believes that continuation would negatively impact the participant's well-being.

Study treatment must be discontinued under the following circumstances:

- Participant/guardian decision
- Pregnancy
- Use of prohibited treatment as per recommendations in the prohibited treatment [Section 6.2.2](#)
- Any situation in which study participation might result in a safety risk to the participant
- Following emergency unblinding
- Severe hypersensitivity reaction such as anaphylaxis
- Adverse events (including AESI, see [Section 10.2.5](#)), abnormal laboratory values or abnormal test result that indicate a safety risk to the participant
- Lack of study treatment effect based on Investigator's judgement
- Patients meeting the discontinuation criteria for liver laboratory triggers or renal alert criteria as defined in [Table 16-4](#) and [Table 16-5](#)

- Study treatment should also be discontinued for any one of the following treatment-emergent events:
  - Absolute QTcF > 500 msec, confirmed by repeat ECG measurements
  - Resting heart rate < 30 or > 120 bpm
  - QRS > 120 msec and increase > 25% from Baseline (Day 1)
  - Sustained ventricular tachycardia lasting 30 sec or more, ventricular fibrillation, or any hemodynamically compromising cardiac arrhythmia
  - New complete heart block (Grade III AV block) or Second degree AV block Mobitz type II

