**16.4 Appendix 4: ECG Alert Threshold Values**

	Patients 18-30 years	Patients Adult > 30 years *
Resting heart rate Sinus rhythm [bpm]	HR < 30 and a HR decrease $\geq$ 25% HR > 130	HR < 40 and a HR decrease $\geq$ 25% HR > 120
QRS duration:		
=> No previous BBB **	> 120 and increase > 25% compared to (predose) baseline	> 120 and increase > 25% compared to (predose) baseline
=> Previous complete BBB * (>120 msec)	> 140 msec	> 140 msec
QTcF	QTcF > 500 msec QTcF increase > 60 msec ***	QTcF > 500 msec QTcF increase > 60 msec ***
Rhythm	Ventricular tachycardia	Ventricular tachycardia
Conduction	New complete heart block (Grade III AV block) Mobitz II AV block	New complete heart block (Grade III AV block) Mobitz II AV block

\* Values displayed also correspond to Severe AE

\*\* BBB = Bundle Branch Block

\*\*\* Normal QTcF with QTc increase > 60 ms may indicate cardiac and non-cardiac pathology, e.g. hypothermia, new BBB, MI, cardiomyopathy or carditis.

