2.6.4 Other safety data

2.6.4.1 ECG and cardiac imaging data

The average triplicate values of 12-lead ECG results and the change in these results from the most recent dose will be summarized for each visit. The absolute value of QTcF will be plotted by box and whisker plot. The incidence of abnormal ECG (see [Table 5-5](#) in appendix) will be presented by treatment arm and by analysis visit and also in listing. The ECG finding will only be presented in listing.

Ambulatory Holter ECG will be recorded for 25 hours for all participants at randomization Day 1 for 25 hours, starting at least 1 hour before the start of the first infusion. Two kinds of device, Holter GI (Global Instrumentation) and Holter patch, will be used in different regions respectively. The abnormality findings from Holter for individual participant will be provided by listing, with the information of the date of first dose, the device type (GI or patch).

[figure not shown]

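### From the second infusion onward, the SAP's ECG change summaries and relative flags no longer refer to Day 1, so gradual individual QTcF change can go unflagged and the protocol's QRS condition is not tabulated as written

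*SAP*

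**What the plan says.** SAP 2.6.4.1 reports averaged triplicate ECG values, and "the change in these results from the most recent dose will be summarized for each visit". It adds that "The absolute value of QTcF will be plotted by box and whisker plot", and that the incidence of abnormal ECGs under Table 5-5 "will be presented by treatment arm and by analysis visit and also in listing".

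Table 5-5 has two columns of flags.
- **Absolute:** these include QRS >109 and >120 msec, and QTcF ≥450 (male), ≥460 (female) and >500 msec.
- **Relative:** these include QRS increases of ≥20% and ≥25%, and QTcF increases of >30 to ≤60 and >60 msec. The footnote gives the reference as "Relative change from previous pre-dosing measurement in percent (%) for RR, PR, QRS", and as "relative change in values compared with previous pre-dosing measurement in millisecond (msec) for QTcF Interval and QT intervals".

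Other safety data in the SAP keep a fixed reference. Vital signs are summarised as change from baseline, with change from the most recent dose added for blood pressure (2.6.4.2). Tables 5-4 (creatinine) and 5-6 (vital signs) are set against baseline. SAP 2.1.1 defines baseline as the last evaluable value before the first dose.

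The protocol uses several references for ECG. Section 9.1.1 lists "QRS > 120 msec and increase > 25% from Baseline (Day 1") and "Absolute QTcF > 500 msec, confirmed by repeat ECG measurements" among the events for discontinuing study treatment. Section 16.4 gives the QRS alert as "> 120 and increase > 25% compared to (predose) baseline" and a QTcF increase above 60 msec with no reference named.

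**The concern.** A reference that moves to the latest pre-dose ECG isolates the acute effect of each infusion, but subtracts whatever change has built up since Day 1. Some drift is plausible. Background antidepressants may be started or adjusted in Screening (Protocol 3.1) and titrated during the first two weeks (Protocol 3.2). Half of the regimen question is whether repeated infusion differs from a single one.

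QT prolongation is an adverse event of special interest, and safety by dose and regimen feeds the Phase 3 selection (SAP 2.11). If each infusion re-zeroes the comparison, the change tables cannot show a cumulative difference between regimens, or identify individuals whose change from Day 1 is large but gradual. The relative QRS flag also stops measuring the quantity in Protocol 9.1.1.

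**Working it through.** The plan states no figure to reproduce. The check sets the references side by side and applies simple arithmetic to hypothetical readings, which are assumptions and not trial data. I take change from the most recent dose to mean change from the ECG taken before the latest infusion, as the Table 5-5 footnote does.

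**Step 1: which reading is the reference.** Core ECG times come from Protocol Table 8-1.

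| ECG | Reference under the SAP | Equal to Day 1? |
|---|---|---|
| Day 1 post-dose, 24 h | Day 1 pre-dose | yes |
| Day 15 pre-dose | Day 1 pre-dose | yes |
| Day 15 post-dose (40 min, 4 h) | Day 15 pre-dose | no |
| Day 29 pre-dose | Day 15 pre-dose | no |
| Day 29 post-dose (40 min, 4 h) | Day 29 pre-dose | no |
| Day 43 | Day 29 pre-dose | no |

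During retreatment the reference is again the latest pre-dose reading, so change from Core Day 1 is not shown there either.

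**Step 2: largest QTcF rise from Day 1 with no relative flag.** A step of 30 msec or less is not flagged.
- Day 15 post-dose or Day 29 pre-dose: 30 + 30 = 60 msec. The >30 to ≤60 category can be missed, but not the >60 category.
- Day 29 post-dose or Day 43: 30 + 30 + 30 = 90 msec. The >60 category can be missed.

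To escape the absolute flag as well, the reading must stay below 450 (male) or 460 (female). A rise above 60 msec does so only if Day 1 QTcF was below 450 − 60 = 390 (male) or 460 − 60 = 400 (female).

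**Step 3: QTcF example, male.**

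| Reading | QTcF (msec) | SAP change | Change from Day 1 |
|---|---|---|---|
| Day 1 pre-dose | 370 | – | – |
| Day 15 pre-dose | 400 | +30 | +30 |
| Day 29 pre-dose | 430 | +30 | +60 |
| Day 29, 4 h | 449 | +19 | +79 |

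No SAP change exceeds 30 and 449 is below 450, so nothing is flagged.

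**Step 4: QRS, relative flag misses.** Change in % = 100 × (reading/reference − 1). Pre-dose values are 96, 108 and 115, then 122 msec at Day 29, 4 h.
- SAP: 108/96 = +12.5%; 115/108 = +6.5%; 122/115 = +6.1%. No relative flag.
- From Day 1: 122/96 = +27.1%, with QRS >120. The condition in Protocol 9.1.1 is met.
- The absolute flags (>109, >120) do fire.

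**Step 5: QRS, relative flag over-calls.** Day 1 pre-dose is 100, Day 15 pre-dose 96, then 121 msec at Day 15, 4 h.
- SAP: 121/96 = +26.0%, flagged ≥25%.
- From Day 1: 121/100 = +21.0%. The protocol condition is not met.

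Table 5-5 also lists QRS >120 and ≥25% as separate flags, whereas Protocol 9.1.1 requires both together and uses >25%.

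**The case against.** The case for leaving the plan alone has substance.

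- **The pre-dose reference is deliberate and useful.** It isolates the acute infusion effect, and the SAP's document history records that it was added on purpose. This stands, and is why those summaries should stay.
- **Absolute flags cover much of the risk.** A reader might infer that a QRS going from 100 on Day 1 to 115 pre-dose and 128 msec post-dose on Day 29 (+28% from Day 1, +11.3% on the SAP's scale) escapes notice. It does not: 128 triggers both >109 and >120. Any analysed ECG that meets the QRS condition must exceed 120 and so carries that flag. Likewise the QTcF >500 msec criterion is absolute and captured.
- **Early drift is caught.** A reader might infer that a 35 msec QTcF drift during antidepressant titration disappears. If it is present by Day 15 pre-dose, it is compared with Day 1 and flagged as >30. Drift escapes the relative flags only when spread over intervals of at most 30 msec each. SoC doses are to be held after week 2 in Core.
- **Participant protection does not depend on these tables.** ECGs are reviewed at site and centrally (Protocol 8.4.3), and the rules in 9.1.1 and 10.2.3 apply in real time. Discontinuations and adverse events of special interest are reported separately.
- **Group drift remains visible** in mean values by visit and the QTcF box plot.
- **Protocol 12.5.2 does not require ECG change from baseline.** It asks for summary statistics and a categorical analysis against predefined limits.

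All of this narrows the point. None of it supplies individual change from Day 1 after the second infusion.

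**Conclusion.** The gap is real but bounded. From the Day 15 post-dose ECG onward, the readable ECG analyses contain no change from Day 1. For QTcF, a participant can be up to 90 msec above Day 1 at Day 29 post-dose or Day 43 without a relative flag. A rise above 60 msec can go wholly unflagged only when Day 1 QTcF was below 390 (male) or 400 msec (female). For QRS, the weakness is classification rather than silence: the >120 flag still fires, but the relative flag can disagree with the Day 1 condition in either direction, and the joint condition is not tabulated.

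How often this would occur is unknown, because the documents give no ECG variability. A reader might infer that the Day 1-based criterion cannot be tabulated at all. That does not follow: Day 1 triplicate ECGs are collected, and the limitation lies in the planned outputs, not the data. Nor do the documents support a claim that participants are left unprotected or that a protocol-specified analysis was dropped. Some neighbouring SAP text is redacted, but 2.6.4.1 and Table 5-5 are readable. The change should be made because it is cheap and bears on an adverse event of special interest.

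**What to change.** - Keep the most-recent-dose summaries and flags for the acute effect.
- In SAP 2.6.4.1, add ECG change from the Day 1 baseline by arm and visit, at least for QTcF and QRS.
- In Table 5-5, add QTcF categories of >30 to ≤60 and >60 msec against Day 1.
- Tabulate the joint QRS condition exactly as Protocol 9.1.1 writes it.
- For retreatment, state whether change is also shown from Core Day 1, from the retreatment baseline, or both.
- Reconcile the reference readings in Protocol 9.1.1, Protocol 16.4 (including the QTcF alert that names none) and SAP Table 5-5. Which clinical rule is right is for the sponsor to settle.

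The cost is about one extra table from ECGs already collected, with no new assessments.
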